### 4.3. OTHER PARAMETERS

#### DEMOGRAPHY AND BASELINE

**Demographic measures:**

- Age
- Sex
- Educational background/ status
- Number of persons living in the household
- Number of children living in the household
- Household net income
- Individual net income

**Baseline variables**

- Attitudes towards psychological online interventions measured with Attitudes towards Psychological Online Interventions Questionnaire (APOI; Schröder et al., 2015)
- Personality measured with Big Five Inventory-10 (BFI-10; Rammstedt et al., 2017)

**Work-related variables**

- Type of healthcare profession
- Number of overtime hours
- Contractually agreed working hours (full-time / part-time -> %)
- Working night shifts yes/no
- Leadership responsibility yes/no

**USER STATISTICS**

- Intervention
- Number of processed modules (in the theory phase) and weekly and daily interventions in the practice phase
- Processing time of the individual contents as well as of the entire intervention
- Contents from the feedback questionnaire, e.g., how well the last module was liked
- Self-care, self-compassion, stress and resilience history / state queries
- Days of usage

**Survey**

- Response times, namely
  - Per questionnaire (how long the user spent on each questionnaire)
  - Total processing time for all questionnaires (after adjustment for interruptions)
- Percentage of missing answers in the questionnaires (absolute and relative to total length of the survey)
- "DEG\_TIME" as normalized indicator for extremely fast completion of questionnaires

**4.4. Hypotheses**

1. The intervention will significantly increase resilience, measured with the SR Score, in the intervention group (IG) compared with a waitlist control (WLC) group at  $t_2$  and  $t_3$  compared to  $t_0$ .
2. The intervention will significantly increase resilience, measured with the Brief Resilience Scale, in the intervention group (IG) compared with a waitlist control (WLC) group at  $t_2$  and  $t_3$  compared to  $t_0$ .
3. The intervention will significantly increase self-care in the intervention group (IG) compared with a waitlist control (WLC) group at  $t_2$  and  $t_3$  compared to  $t_0$ .
4. The intervention will significantly increase self-compassion in the intervention group (IG) compared with a waitlist control (WLC) group at  $t_2$  and  $t_3$  compared to  $t_0$ .
5. The intervention will significantly increase mindfulness in the intervention group (IG) compared with a waitlist control (WLC) group at  $t_2$  and  $t_3$  compared to  $t_0$ .
6. The intervention will significantly reduce perceived stress in the intervention group (IG) compared with a waitlist control (WLC) group at  $t_2$  and  $t_3$  compared to  $t_0$ .
7. The intervention will significantly increase mental health in the intervention group (IG) compared with a waitlist control (WLC) group at  $t_2$  and  $t_3$  compared to  $t_0$ .
8. The intervention will significantly reduce depressive symptoms in the intervention group (IG) compared with a waitlist control (WLC) group at  $t_2$  and  $t_3$  compared to  $t_0$ .
9. The intervention will significantly reduce anxiety symptoms in the intervention group (IG) compared with a waitlist control (WLC) group at  $t_2$  and  $t_3$  compared to  $t_0$ .
10. The intervention will significantly reduce burnout symptoms in the intervention group (IG) compared with a waitlist control (WLC) group at  $t_2$  and  $t_3$  compared to  $t_0$ .
11. The intervention will significantly increase work-life-balance in the intervention group (IG) compared with a waitlist control (WLC) group at  $t_2$  and  $t_3$  compared to  $t_0$ .
12. In the intervention group, the intervention will lead to improved resilience by the end of the intervention (at  $t_2$ ) and these improvements should be maintained at the respective follow-ups (at  $t_3$ ,  $t_4$ ,  $t_5$ ; probably to a lesser degree).
13. Self-compassion interventions (weekly intervention and daily training intervention) in the practice modules:
  - A) For the weekly interventions, the state self-compassion measure will be significantly higher after the interventions (comparison of  $st_{2.1pre}$  vs.  $st_{2.1post}$  and  $st_{4.1pre}$  vs.  $st_{4.1post}$ ).
  - B) For the first session of the daily training interventions, the state self-compassion measure will be significantly higher after the interventions (comparison of  $st_{2.2pre}$  vs.  $st_{2.2post}$  and  $st_{4.2pre}$  vs.  $st_{4.2post}$ ).
14. Self-care interventions (weekly intervention and daily training intervention) in the practice modules:
  - A) For the weekly interventions, the state self-compassion measure will be significantly higher after the interventions (comparison of  $st_{1.1pre}$  vs.  $st_{1.1post}$  and  $st_{3.1pre}$  vs.  $st_{3.1post}$ ).
  - B) For the first session of the daily training interventions, the state self-compassion measure will be significantly higher after the interventions (comparison of  $st_{1.2pre}$  vs.  $st_{1.2post}$  and  $st_{3.2pre}$  vs.  $st_{3.2post}$ ).
15. For the intervention group, the number of weekly interventions and daily training interventions completed will result in a significant
  - A) increase of self-care at  $t_2$
  - B) increase of self-compassion at  $t_2$
  - C) increase of resilience measured with SR score at  $t_2$
  - D) decrease of burnout symptoms at  $t_2$

Further longitudinal effects, intervention effects at intermediate measurements ( $t_1$ ), other resilience-related outcomes as well as moderator and mediator analyses will be examined exploratorily. Therefore, no specific hypotheses are stated.

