### 1.2. SECONDARY OBJECTIVES

Secondary objectives are to find out whether the intervention is effective in increasing the addressed health-related and resilience factors (e.g., optimism) as well as decreasing self-evaluations of psychopathological indicators (e.g., depression, anxiety) in healthcare professionals. Also, the study investigates whether different interventions are effective in changing state-measures of health-related self-evaluations.

Another objective is to investigate these effects in the long term (up to one-year post-intervention).

Additionally, feasibility and usability of the intervention and the newly developed platform resiLIR will be investigated.

Further objectives are to examine exploratorily the influence of the intervention on other resilience-related outcomes, mental health literacy, health seeking behaviour and stigma against mental illness and to conduct network analyses.

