### 2.1. STUDY DESIGN

Randomized Controlled Trial with 240 participants working as healthcare professionals (120 in intervention, 120 in waitlist control group), monocentric study, duration: 14 months, study design chosen to evaluate long-term effects of our training)

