### 2.2. TREATMENT GROUPS

Treatment: Participants in the intervention group will gain access to the 6-week online resilience intervention "resiLIR Healthcare Professionals".

The waitlist control group will receive access to the intervention after the first follow-up assessment (3 months post-intervention).

Randomisation process: Stratified randomization is used, with age and gender as influencing factors. Randomization is performed using randomized numbers generated with Microsoft Excel. Due to the nature of the intervention, no blinding and subject replacements are planned.

Subject replacement: not applicable.

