### 2.6. STUDY PROCEDURE

Once the desired sample size has been reached, a randomized controlled trial with 6 measurement time points will be conducted in which participants will be randomly assigned to either the intervention group or the waiting control group.

The intervention group receives access to the online training after randomization. The waiting control group receives access only after the first follow-up measurement (3 months after the post-measurement). Two further follow-up measurements follow (6 and 12 months after the post-measurement). The detailed time schedule can be seen in the attached flow chart. The entire data collection and intervention will be online. Neither the participants nor the study team will be blinded.

Within the practice modules, the following interventions and measurements are planned (in weeks 3 and 5, a self-care intervention is planned, in weeks 4 and 6, a self-compassion intervention is planned):

Practice phase: trainings and measurements (weeks 3 to 6; with buffer to complete the modules for weeks 7 & 8)				
Week 3	Day 1	st 1.1 pre state assessment pre-intervention	Weekly intervention (approx. 30 min)	st 1.1 post state assessment post-intervention
	Day 2	st 1.2 pre state assessment pre-intervention	Daily training intervention, 1st session (approx. 5-10 min)	st 1.2 post state assessment post-intervention
	Day 3	st 1.3 pre	Daily training intervention, 2nd session (approx. 5-10 min)	st 1.3 post
	Day 4	st 1.4 pre	Daily training intervention, 3rd session (approx. 5-10 min)	st 1.4 post
	Day 5	st 1.5 pre	Daily training intervention, 4th session (approx. 5-10 min)	st 1.5 post
	Day 6	st 1.6 pre	Daily training intervention, 5th session (approx. 5-10 min)	st 1.6 post
	Day 7	st 1.7 pre	Daily training intervention, 6th and last session (approx. 5-10 min)	st 1.7 post
Week 4	Day 1	st 2.1 pre state assessment pre-intervention	Weekly intervention (approx. 30 min)	st 2.1 post state assessment post-intervention
	Day 2-7	st 2.2 pre- st 2.7 pre	Daily training intervention, 2nd – 6th session (approx. 5-10 min)	st 2.2 post- st 2.7 post
Week 5 - 6	...	...	...	...

Legend: stx.x pre = state assessment pre-intervention; stx.x post = state assessment post-intervention

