### 5.2. PRIMARY AND SECONDARY DATA ANALYSES

In primary and secondary data analyses, all stated hypotheses will be tested. In all analyses an error probability of  $\alpha = .05$  will be set a priori for interference statistics calculations. In cases of multiple testing,  $\alpha$  will be adjusted accordingly. In addition to statistical significance, descriptive statistics and effect sizes (e.g., Cohen's  $d$ ) will be reported. Publication of results will follow CONSORT guidelines for transparent reporting of randomized trials.

Cronbach's  $\alpha$  and McDonald's  $\omega$  will be calculated as measure of reliability of the respective questionnaires.

Before data analysis, assumptions of statistical methods (e.g., variance of homogeneity, normal distribution) will be tested with suitable procedures (e.g., Levene-tests, Box's M, histograms, QQ-plots, and Shapiro-Wilk-Test). Zero-order correlations between study variables will be reported. Non-parametric correlation calculation will be based on results of (non-)normality, etc. Variables will be standardized where applicable.

The analysis plan for H1 to H11 is as follows:

- Differences between study groups in primary and secondary outcomes before ( $t_0$ ) and after the intervention ( $t_2$ ) and at the time of the first follow-up ( $t_3$ ) will be examined using mixed analyses of covariance (ANCOVA), with group (intervention vs. waitlist-control) as a between-subjects factor, time ( $t_0$ ,  $t_2$ ,  $t_3$ ) as a within-subjects factor and pre-measurement ( $t_0$ ) included as a covariate to increase test power. Outcomes will be the primary outcome resilience (measured with SR Score) and the secondary outcomes resilience (measured with BRS), perceived stress, self-care, self-compassion, mindfulness, mental health, depression, anxiety, burnout, and work-life-balance, respectively.
- If applicable, post-hoc  $t$ -tests will be conducted.
- Effect sizes will be calculated for the ANCOVA (i.e.,  $\text{Eta}^2$ ) as well as for between-group differences (i.e., Cohen's  $d$ ) at post-intervention assessment ( $t_2$ ) and the first follow-up assessment ( $t_3$ ). Also, the effect size of the intervention effect will be calculated (i.e., Cohen's  $d$ ).

The analysis plan for H12 is as follows: term effect over the follow-up measurements ( $t_0$  to  $t_5$ ) within the intervention group will be tested using a repeated measures ANOVA.

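### H12 credits the intervention with resilience gains up to 12 months but is tested in the intervention arm alone; the design gives a controlled effect only to 3 months after the intervention

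*SAP*

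**What the plan says.** **Aim.** SAP 1.2 lists as a secondary objective: "Another objective is to investigate these effects in the long term (up to one-year post-intervention". SAP 2.1 describes the "study design chosen to evaluate long-term effects of our training".

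**Comparator.** SAP 2.2: "The waitlist control group will receive access to the intervention after the first follow-up assessment (3 months post-intervention". SAP 2.6 adds: "Two further follow-up measurements follow (6 and 12 months after the post-measurement". The schedule is therefore t0 (before), t2 (after), t3 (3 months), waitlist trained, t4 (6 months), t5 (12 months).

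**Controlled hypotheses.** H1 to H11 compare intervention and waitlist at t2 and t3 against t0. H1 (SR score) and H2 (Brief Resilience Scale) concern resilience. SAP 5.2 analyses them with group as a between-subjects factor and time points t0, t2 and t3.

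**H12.** SAP 4.4: "In the intervention group, the intervention will lead to improved resilience by the end of the intervention" (t2), and "these improvements should be maintained at the respective follow-ups" (t3, t4, t5). By SAP 5.2, the course from t0 to t5 "within the intervention group will be tested using a repeated measures ANOVA".

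**The concern.** H12 is worded as cause and effect, but its test has no comparator. The test answers whether resilience changed over time in people who had the training. It does not answer whether the training changed it. Choosing a different within-arm test or contrast would not help, because the missing element is the control group.

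Two consequences follow. At t2 and t3 a randomised untreated control exists and H12 does not use it, so H12 could be declared confirmed while H1 and H2 show no effect. The plan has no rule for that conflict. At t4 and t5 no untreated control is left, so a maintained effect at 12 months could be reported with nothing in the design to separate it from change that would have occurred anyway.

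**Working it through.** **1. What each time point can support**

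| Time point | Waitlist status | H1/H2 comparison | H12 test |
|---|---|---|---|
| t2 (post) | untreated | randomised | intervention arm only |
| t3 (3 months) | untreated | randomised | intervention arm only |
| t4 (6 months) | offered training | none planned | intervention arm only |
| t5 (12 months) | offered training | none planned | intervention arm only |

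The controlled effect ends at t3, while the objective in 1.2 runs to one year. H12 is not conditional on H1 or H2. It is a numbered hypothesis, and SAP 5.2 says that all of these are tested. The closing remark of 4.4, which makes certain analyses exploratory, concerns further longitudinal effects and so does not cover H12.

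**2. How often the H12 comparison is significant with no intervention effect**

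The plan states no figure on this point, so there is none to reproduce.

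Inputs from the SAP:
- 120 per arm and 40% dropout (2.5), so 120 × 0.6 = 72 completers. I use n = 72, and n = 120 for full retention.
- Alpha 0.05 (5.2), taken here as two-sided.

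Assumptions that the SAP does not give:
- A shift d from t0 of 0.1, 0.2 or 0.3 SD that would occur without training.
- A within-person correlation r of 0.5 to 0.7.

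Method: a paired t-test of t0 against one follow-up, unadjusted, with power from the noncentral t distribution.

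- Standardised mean change: dz = d / √(2(1 − r))
- Noncentrality: dz × √n, on n − 1 degrees of freedom

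Example: d = 0.2, r = 0.6, n = 72. dz = 0.2/√0.8 = 0.224. Noncentrality = 0.224 × √72 = 1.90, and the critical t on 71 df is 1.99. The probability of a significant improvement is 0.46. At n = 120 the noncentrality is 2.45 and the probability 0.68.

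| Drift | n = 72 (r = 0.5 to 0.7) | n = 120 (r = 0.5 to 0.7) |
|---|---|---|
| 0.1 SD | 0.13 to 0.19 | 0.19 to 0.29 |
| 0.2 SD | 0.39 to 0.58 | 0.58 to 0.80 |
| 0.3 SD | 0.71 to 0.90 | 0.90 to 0.99 |

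**3. The planned omnibus test**

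The one-group repeated measures ANOVA over six time points was simulated (4,000 runs, compound symmetry, full drift from t2 onward and half at t1, n = 72, r = 0.5 and 0.7). It rejects with probability 0.10 to 0.16, 0.36 to 0.58 and 0.74 to 0.93 for drifts of 0.1, 0.2 and 0.3 SD, against about 0.05 with no drift.

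**4. The randomised contrast under the same drift**

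A two-group test of change scores (n = 72 per arm, r = 0.5) rejects in 0.049 to 0.057 of simulations for drifts of 0, 0.2 and 0.3 SD. The drift is common to both arms and cancels. This contrast is available only up to t3.

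**5. Effect of adjusting alpha**

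SAP 5.2 says that alpha will be adjusted in multiple testing but names no method. If that meant Bonferroni over the four contrasts of t0 with t2 to t5 (0.05/4 = 0.0125), the example values 0.46 and 0.68 would fall to 0.26 and 0.47.

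**The case against.** The best defence is that the plan already separates efficacy from course. H1 and H2 test resilience on the randomised contrast, every controlled comparison stops before the waitlist is trained, and H12 says openly that it concerns the intervention group. Between-group effect sizes at t2 and t3 and results by arm would be reported, so a null H1 beside a confirmed H12 would be visible. Crossover after t3 is inherent in a waitlist design, and the remark in 2.1 may only explain the length of follow-up.

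Much of this stands. The primary hypothesis and the randomised analyses are untouched, and nothing suggests that arm differences at t4 or t5 would be read as training against no training. But visibility does not cure the fault: H12 is a separately tested hypothesis with causal wording, and it does not depend on H1 or H2.

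The numbers also need care. A within-group test that detects a real change is not in error; the error lies in attributing the change to the training. Drift and correlation are assumed, and the paired test is a follow-up to the planned ANOVA.

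A reader might infer more than the SAP supports:
- *That natural change will be counted as benefit.* It can only be said that the two cannot be separated; drift could equally hide a benefit.
- *That regression to the mean is a main driver.* SAP 2.3 sets no stress or symptom threshold for entry, so it may be modest.
- *That season is fully confounded with time since training.* t2 and t5 are 12 months apart, so season largely cancels between them, though not between t0 and t2, t3 or t4. A simultaneous start for everyone is only one reading of "Once the desired sample size has been reached, a randomized controlled trial with 6 measurement time points will be conducted" (2.6).

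**Conclusion.** The point holds. H12 attributes improvement and its maintenance to the intervention on a test that cannot support attribution, and it can be confirmed with H1 and H2 null. The design supports a controlled effect to 3 months after the intervention; the one-year effects in 1.2 and 2.1 lie beyond that.

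This conclusion rests on the SAP's own text and needs no assumed figure. The probabilities (0.13 to 0.90 at n = 72, 0.19 to 0.99 at n = 120) show only how readily a modest common drift would produce a positive H12. They depend on the assumed drift, correlation and unadjusted test, and fall if alpha is adjusted. The matter should be corrected before analysis; it does not threaten the primary comparison.

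**What to change.** - **H12 at t2 and t3:** let the claim that the intervention improves resilience rest on the randomised comparisons in H1 and H2.
- **H12 at t4 and t5:** reword as the uncontrolled within-group course after training, reported with estimates and confidence intervals. Read it as maintenance only if the randomised effect at t2 has been shown, and do not call it an intervention effect.
- **Context:** show the waitlist's course from t0 to t3 beside it.
- **Sections 1.2 and 2.1:** state that controlled effects are evaluated to 3 months after the intervention and that uncontrolled follow-up runs to 12 months.

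The cost is SAP wording and one descriptive table from data already planned. Visits, sample size and the waitlist's access to training stay as they are. The downside is a more modest 12-month claim.

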- If applicable, post-hoc  $t$ -tests and planned contrasts will be conducted.
- Effect sizes will be calculated.
- $\text{Eta}^2$  will be calculated as measure for effect size for the ANOVA.

The analysis plan for H13 and H14 is as follows:

- In order to test whether the changes in the state measurements (pre- to post-intervention in state self-compassion and state self-care) are significant, we will conduct within-group  $t$ -tests. We will perform separate tests for state self-compassion and state self-care, each for (1) the weekly training interventions and (2) the first practice of daily interventions, respectively.
- Cohen's  $d$  will be calculated as measure for effect size.

The analysis plan for H15 is as follows:

- Linear regressions will be conducted with the following predictor and criterion variables:
  - Predictor variables:
    - baseline-values of self-care (and, in separate models, self-compassion / resilience / burnout, respectively) at  $t_0$
    - amount of interventions completed (number of weekly training interventions and daily interventions)

- Criterion variables:
  - Post-intervention values of self-care (and, in separate models, self-compassion / resilience / burnout, respectively) at  $t_2$

If assumptions for the mentioned statistical methods are violated, appropriate non-parametric statistical methods will be chosen.

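### H15 words a self-chosen amount of exercise as the cause of better t2 outcomes and adjusts only for the t0 value, so confounding with usage may appear as a dose effect

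*SAP*

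**What the plan says.** In SAP section 4.4, H15 reads "For the intervention group, the number of weekly interventions and daily training interventions completed will result in a significant", followed by an increase in self-care (A), self-compassion (B) and SR-score resilience (C) and a decrease in burnout (D), all at t2.

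Section 5.2 gives one linear regression per outcome. The predictors are "baseline-values of self-care (and, in separate models, self-compassion / resilience / burnout, respectively") at t0, and "amount of interventions completed (number of weekly training interventions and daily interventions"). The criterion is "Post-intervention values of self-care (and, in separate models, self-compassion / resilience / burnout, respectively") at t2. No other covariate is listed. Section 5.2 also says that every stated hypothesis is tested in the primary and secondary analyses, so H15 is not exploratory.

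Section 4.3 lists variables that could bear on both usage and outcome: "Number of overtime hours", "Contractually agreed working hours", "Working night shifts yes/no" and, among the baseline variables, "Attitudes towards psychological online interventions measured with Attitudes towards Psychological Online Interventions Questionnaire" (APOI). The only uses stated for the work-related variables are descriptive reporting and the baseline comparison of the groups (section 5.1). Attitude to online interventions appears again only as an example of an exploratory moderator or mediator (section 5.3).

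**The concern.** Randomisation decides who gets access to the training (section 2.2). It does not decide how many weekly and daily exercises a participant completes. H15 is thus a causal statement about an exposure that nobody assigns, tested within one arm, where randomisation gives no protection.

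In working health care staff, a heavy load could both reduce the exercises completed and worsen burnout or self-care over the same weeks. A favourable view of online training could raise both usage and self-reported benefit. Either would tilt the usage slope towards H15 even if dose did nothing. Adjusting for the t0 value removes the part of such influences already expressed at t0, but not the part that acts on change from t0 to t2. Four planned claims depend on this model, and a positive result would naturally be read as support for the training.

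**Working it through.** The SAP gives no sample size, power or effect size for H15, so there is no figure of its own to reproduce. The check asks how often the planned regression would reject if dose had no effect.

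**Inputs from the SAP**
- n = 120 in the intervention group (section 2.5), or 120 × (1 − 0.40) = 72 after the assumed dropout.
- Significance level 0.05 (sections 2.5 and 5.2), taken here as two-sided.
- Model: t2 value on t0 value and amount completed, the latter taken as one count.

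**Assumed, because the SAP gives none of them**
- Workload correlates −a with usage, c0 with the t0 outcome and c2 with the t2 outcome (burnout, for illustration).
- The t0–t2 correlation is r = 0.6.
- Usage relates to the outcome only through workload, so the true dose effect is zero.

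**Formula.** The spurious partial correlation of usage with the t2 value, given the t0 value, is

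ρ = −a (c2 − r·c0) / √[(1 − a²c0²)(1 − r²)].

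The test statistic has n − 3 degrees of freedom and noncentrality δ = |ρ| √(n − 3) / √(1 − ρ²). Three cases matter:

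1. Workload acts only through the t0 value: c2 = r·c0, so ρ = 0. The planned model is unbiased.
2. Workload is stable and equally correlated with both time points: c0 = c2 = c, so ρ = −a·c(1 − r) / √[(1 − a²c²)(1 − r²)].
3. Workload is unrelated to t0 and acts only on change, with correlation b to the t2 value given t0: ρ = −a·b.

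**Worked example**, a = 0.5 and c or b = 0.4:
- Case 2: |ρ| = 0.5 × 0.4 × 0.4 / √(0.96 × 0.64) = 0.08 / 0.784 = 0.102. At n = 72, δ = 0.102 × √69 / 0.995 = 0.85 and rejection is 13.4%. At n = 120, δ = 0.102 × √117 / 0.995 = 1.11 and rejection is 19.6%.
- Case 3: |ρ| = 0.20. At n = 72, δ = 0.20 × √69 / √0.96 = 1.70 and rejection is 38.7%. At n = 120, δ = 2.21 and rejection is 59.1%.

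Rejection rates, two-sided 5%, zero dose effect, n = 72 / n = 120:

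| Assumed a and c (or b) | Case 2: stable workload | Case 3: acts only after t0 |
|---|---|---|
| 0.2, 0.2 | 5.3% / 5.5% | 6.2% / 7.1% |
| 0.3, 0.3 | 6.6% / 7.7% | 11.5% / 16.3% |
| 0.4, 0.4 | 10.2% / 14.1% | 26.4% / 41.3% |
| 0.5, 0.4 | 13.4% / 19.6% | 38.7% / 59.1% |

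A simulation with 20,000 replicates per cell agrees to within about one percentage point. For the last row of case 2, moving r from 0.5 to 0.7 moves the rates from 16.3% / 24.7% to 10.9% / 15.2%.

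**Multiplicity.** Section 5.2 adjusts alpha for multiple testing without naming a method. If the four H15 tests were each run at 0.05 / 4 = 0.0125, the last row becomes 4.8% / 8.1% (case 2) and 20.0% / 37.5% (case 3), against a nominal 1.25%. The rates fall, but the slope stays biased.

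**With workload in the model**, the partial correlation is zero and rejection returns to about 5%. That follows by construction: here workload is the only confounder and is measured without error.

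**The case against.** The strongest reply is that the t0 adjustment already does most of the work. Contracted hours and night shifts, and to a degree overtime, are fairly stable job features listed with the baseline data, so they should already have shaped the t0 value. This largely stands. It is why case 2 is the more natural reading for these variables and why its rates are far below those of case 3. With stable workload and r = 0.6, a correlation of 0.4 given t0 needs a cross-sectional correlation of about 0.62 to 0.63 (0.62 × 0.4 / √(0.6156 × 0.64) = 0.395; 0.63 × 0.4 / √(0.6031 × 0.64) = 0.406).

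A reader might infer that overload will show up as a dose effect, that all four claims are likely to be confirmed falsely, and that adding the workload items cures this. The documents support none of these. No section reports how workload relates to usage. Staff under rising strain might practise more, which would reverse the bias. Joint confirmation of the four outcomes cannot be computed from the SAP. Nor can the listed items capture overload that arises during the training, motivation, or early improvement or worsening.

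It can also be said that the SAP recognises usage as an issue. Section 5.1 examines it as an exploratory covariate to control for compliance, and section 5.3 names it, with attitude to online interventions, among possible moderators or mediators. Those analyses do not adjust the H15 usage slope for the causes of usage, and no section limits H15 to an association.

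**Conclusion.** The point holds as one of wording, model and interpretation for a subsidiary hypothesis. H15 makes a causal claim that its regression cannot support, because usage was not randomised and only the t0 value is adjusted for. That conclusion does not depend on any assumed correlation.

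The size does depend on them. The false-positive rate is nominal if workload acts only through t0, about 5% to 20% over the range examined if workload is stable (r = 0.6), and about 39% to 59% only at the strong end of the case where workload acts solely on change after t0. All of these fall after the alpha adjustment. The direction is plausible but not established. H1 to H11 rest on the randomised comparison and are untouched.

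**What to change.** 1. In section 4.4, reword H15 so that the number of exercises completed 'will be associated with' the t2 outcomes. State that H15 supports no causal dose-response conclusion because usage was not randomised. This step carries the fix.
2. In the H15 part of section 5.2, add the baseline covariates already collected to each of the four regressions: overtime hours, contracted hours, night shifts, APOI score, and age and gender (the randomisation factors). Naming them now avoids choosing an adjustment set after seeing the data.
3. State beside them that this removes only measured baseline confounding and leaves motivation, overload arising during the training and early response uncontrolled.

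The cost is a short SAP edit, a few degrees of freedom out of 72 to 120 participants, and a weaker claim. No new data are needed.
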